- Compare the diagnostic capability of two different methods of rhythm screening – time-limited patch ECG monitoring versus long-term wearable pulse wave monitoring through photoplethysmography – for AF detection and tolerability.

Influence on Clinical Care

- Compare the rate of initiation of anticoagulation and other AF-specific therapies at 12-months in the active monitoring cohort versus the matched observational control cohort.
- Compare the overall incremental costs of active monitoring for AF detection versus standard of care in the 3 years following the onset of monitoring.
- Identify the impact of active AF screening versus routine care on the time to first event of the following endpoints using claims data; A) among individuals diagnosed with new AF at 3 years following the initiation of screening, and B) the entire study cohort: utilizing claims data.
 - The combined endpoint of stroke/TIA, other systemic embolization, and/or myocardial infarction.
 - In the Medicare population only, in who mortality data will be available, the combined endpoint of stroke/TIA, other systemic embolization, myocardial infarction and/or death
 - The individual components of the combined endpoint.
 - All hospitalizations.
 - Hospitalizations for bleeding events.

4. Study Design

Participants

The study population will be derived from the Aetna Commercial Fully Insured and Medicare populations. From this population specific characteristics associated with an increased proportion of prevalent atrial fibrillation will be identified through claims data and utilized to identify a population at increased risk for undiagnosed atrial fibrillation.

Inclusion Criteria:

- Male or female age > 75 or
- Male age > 55, or female age > 65, and
- Prior CVA, or
- Heart failure, or
- Diagnosis of both diabetes and hypertension, or
- Mitral valve disease, or
- Left ventricular hypertrophy, or
- COPD requiring home O2, or
- Sleep apnea, or
- History of pulmonary embolism, or
- History of myocardial infarction, or
- Diagnosis of obesity

Exclusion Criteria:

- Current or prior diagnosis of atrial fibrillation, atrial flutter or atrial tachycardia
- Receiving chronic anticoagulation therapy
- Hospice care
- End stage renal disease
- Diagnosis of moderate or greater dementia
- Implantable pacemaker and/or defibrillator
- History of skin allergies to adhesive patches
- Known metastatic cancer

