During the 4-month monitoring period all individuals will undergo continuous single-lead ECG monitoring with a wearable patch (iRhythm ZIO® XT Patch) during the first and last 2 weeks of the 4-month study period (total of 4 weeks).

Consenting participants will also be invited to participate in a ~500 person sub-study to wear an additional monitoring device; a wristband photoplethysmography-based device (Amiigo). Enrollment in this sub-study will be limited to individuals who already own and use a smartphone (iOS or Android). Volunteers will be asked to sign a second informed consent to participate in this sub-study.

Monitoring Devices

All individuals randomized to active screening will receive a ZIO XT Patch (<http://www.irhythmtech.com/zio-solution/zio-patch/>). The ZIO XT Patch will be mailed to the participant's home with instructions how to place and activate the patch. A link to an instructional video will also be provided as well a call-in number for support.

They will be asked to wear it for the first 2 weeks, and again during the final 2 weeks of the 4-month monitoring period. While wearing the patches a single-lead ECG is recorded

continuously. After the 2-week monitoring period the patch is mailed back to iRhythm in a pre-prepared package where the rhythm is analyzed.

A second exploratory method of rhythm detection in a self-identified subset of the same patients will be carried out using a wristband developed by Amiigo (<https://amiigo.com/>) that will allow for long term, non-obtrusive monitoring on a daily basis throughout the 4 month period. The Amiigo determines resting pulse rate using photoplethysmography; a technique

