2. Time to first event of stroke, systemic emboli, or myocardial infarction in the sub-population of individuals diagnosed with AF in the 2 cohorts, as well as within the entire cohorts during 3 years of follow-up. For the Medicare population in who reliable mortality data are available the time to first event of stroke, systemic emboli, myocardial infarction or death will also be evaluated.
 - Time to first event of individual components of the combined endpoint.

3. Cost effectiveness outcome is a key analysis but because of the many unknowns surrounding event rates, and changes in therapy at the time of diagnosis a Bayesian approach seems most appropriate. The initial determination of cost effectiveness will be limited to those diagnosed with AF by 3 years using available claims data. A secondary analysis can evaluate the entire study population comparing a monitored approach to standard of care.
4. Exploratory analysis of the efficacy of the Amigo wristband in detecting AF relative to ECG confirmation by ZIO XT Patch.

Safety Endpoints

1. Incidence of hospitalization for a primary bleeding diagnosis.
2. Incidence of the detection of non-AF, but other actionable heart rhythm issues during monitoring.
3. Incidence, timing and etiology of early discontinuation of active monitoring.

Endpoint Data Dictionary

1. Atrial Fibrillation/Flutter: Diagnosis of atrial fibrillation or atrial flutter confirmed via the Aetna Informatics Health Profile Database (HPD). The HPD is a foundation database used to identify Aetna members with chronic diseases or medical conditions. The identification algorithms are comprised of medical, pharmacy, and clinical laboratory data from physician claims and encounters, specialist claims, pharmacy, facilities, laboratories and others.
2. Each of the end-points listed below will be identified using ICD9/ICD10 codes within the adjudicated inpatient or ER medical case.
 - a. Transient ischemic attack / Stroke
 - b. Myocardial infarction
 - c. Arterial thromboembolism
3. Hospital admitting, discharge and transfer (ADT) information will be used to identify hospitalizations, and length of stay.

4. Drug NDC codes will be used to identify new refill for any anticoagulant (dabigatran, rivaroxaban, apixaban) or P2Y12 antagonists (clopidogrel, prasugrel or ticagrelor).
5. Mortality will be determined based on the latest Aetna membership tables and hospital discharge status.

7. Statistical Considerations

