4 month assumptions: 5% incidence AF in monitored, 0.5% in non-monitored.

[figure not shown]
	Sample Size Active Monitoring	Sample Size Delayed Monitoring	Event Rate Active Monitoring	Event Rate Delayed Monitoring	Power
As Designed	1000	1000	5%	0.5%	>0.99
Minimal Size	320	320	5%	0.5%	0.90
Minimal Size, Increased Event Rate	430	430	5%	1.0%	0.90

12 months assumptions: 7% incidence AF in monitored, 2% in the observational control arm.

	Sample Size Active Monitoring	Sample Size Matched Observational Cohort	Event Rate Active Monitoring	Event Rate Delayed Monitoring	Power
As Designed	2000	4000	7%	2%	>0.99
Minimal Size	400	400	7%	2%	0.90
Minimal Size, Increased Event Rate	1278	1278	7%	4%	0.90

3-year assumptions:

- 10% prevalence of AF in both monitored and observational control arms.
- A 7.5% event rate in observation cohort (based on ACTIVE A data) and a 50% reduction in the monitored cohort due to earlier diagnosis prior to having an event or symptom.

Power = 0.81 for log rank test with assumptions as below (rates are cumulative):

	Actively Monitored		Control	
Sample size with AF (10% prevalence in both groups)	n=200		n=400	
	Diagnosis Rate	Event Rate	Diagnosis Rate	Event Rate
6 months	5%	1%	0.5%	4%
15 months	7%	2%	3%	9%
36 months	10%	5%	10%	12%

A separate, detailed statistical analysis plan will be developed.

8. Possible Benefits

It is possible that participants could benefit by receiving a diagnosis of AF before they would otherwise, which could possibly lead to changes in therapy that might decrease their risk of thromboembolic events.

As determining the optimal method for population screening for AF is recognized as being an important unmet need, the results of this study could benefit a substantial proportion of the population through helping identify and refine screening methods. In addition, participation in this study will provide a greater understanding of the characteristics (e.g. frequency, duration, rate, time of day) of arrhythmias episodes that are or are not associated with symptoms.

9. Possible Risks and Analysis of Risk/Benefit Ratio

There is minimal risk to a patient receiving cardiac rhythm monitoring and, in general, complications are related to the adhesive that affixes the ZIO XT Patch to the subject. The FDA has cleared the ZIO XT Patch for use for patients who do not have known skin allergies or a family history of skin allergies. Company experience for skin allergies in 2011 is 0.02% in over 30,000 patients.

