Findings during monitoring may require therapies only a physician can provide to prevent potentially serious complications. Therefore if a participant chooses not to share their physicians contact information with the study team they are potentially placing them at increased risk. All such participants will be informed, verbally and in writing, of their sole responsibility to inform their physician and the potential risk if they don't.

There are no known risks associated with wearing the Amiigo wristband. Because the Amiigo wristband has not yet been validated for heart rhythm detection there is a risk that a real heart rhythm problem may not be detected or that when a heart rhythm problem is thought to be detected it may not be real. Also, all data from the Amiigo device will be analyzed by Amiigo and although all attempts will be made to assure their privacy and security it is not possible to guarantee their security.

Additional risks to the patient include the potential for emotional or mental discomfort of knowingly wearing a cardiac rhythm monitor for an extended period of time. We consider this risk to be quite low.

Study subjects are not expected to receive a direct benefit from participating in this study but they can keep the device, the charger, download the free commercially available Amiigo App, and continue self-monitoring. The study app will be inactivated.

The control arm will receive current standard of care.

10. Risk Management Procedures

Loss of privacy

Participants will be identified by a 4-digit study ID. Only the investigators and research staff will have access to the patient's fully identified medical information. The information that matches the code to the identifying information will be kept in a safeguarded database that is password protected. Any paper files, such as ECG print outs will be kept in a secure location at STSI without identifying information.

11. Subject Payment/Costs

Subjects will not be directly remunerated for participation in the study. There is no cost to the subject for study participation.

12. Estimated Duration of Study

Participant's active involvement in the study will be 4 months. Clinical endpoints will be collected passively up to 3 years after study initiation. However, the study participants or their physicians may be contacted up to 3.5 years after study initiation to confirm vital status and locate any critical missing data.

13. Consent Procedures

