7. STATISTICAL METHODOLOGY

Sample Size Determinations

For the 4-month RCT, the sample size of 1,000 subjects for each group (immediate monitoring = active monitoring and delayed monitoring=no active monitoring) achieves >99% power to find a difference between an expected incident atrial fibrillation rate of 5% in the active monitoring group and an expected incident atrial fibrillation rate of 0.5% group without active monitoring with a two-sided alpha of 0.05. This sample size also achieves adequate power for the detection of the difference between the two groups at lower event rates, achieving 98% power for an expected rate of 2% in the active monitoring group and 0.1% in the delayed monitoring group with a two-sided alpha of 0.05.

For the Matched Observational Cohort Study, at 12 months, sample sizes of 2,000 subjects in the active monitoring group (immediate monitoring + delayed monitoring) and 4,000 subjects in the matched control group achieves >99% power to find a difference in the expected atrial fibrillation rate of 7% in the active monitoring group and 2% in the matched control group with a two-sided alpha of 0.05.

For the Matched Observational Cohort Study, based on an expected prevalence of atrial fibrillation of 10% in both the actively monitored (i.e., n=200) and matched control cohorts (i.e, n=400), a 7.5% event rate/year in the matched observational cohort and a 50% reduction in events in the actively monitored cohort due to earlier diagnosis prior to having an event or symptom, the expected combined event rate is 5% in the actively monitored subjects and 12% in the matched observational controls. Given these assumptions, the sample size yields 81% power to detect the expected difference in time to event with a log rank test with a two-sided alpha of 0.05.

Descriptive Statistics

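### The only firmly planned cost-effectiveness analysis is confined to people diagnosed with AF, so it does not estimate the overall incremental cost of screening that both documents set as the objective

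*Protocol*

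**What the plan says.** The cost objective appears in Protocol Section 3 (Influence on Clinical Care) and again, in the same words, in SAP Section 1: "Compare the overall incremental costs of active monitoring for AF detection versus standard of care in the 3 years following the onset of monitoring". The comparison is between monitoring and usual care. It is not restricted to people who turn out to have AF.

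Protocol Section 6, secondary efficacy endpoint 3, gives the analysis. It opens "Cost effectiveness outcome is a key analysis but because of the many unknowns surrounding event rates", and proposes a Bayesian approach for that reason. It then sets the population and data source: "The initial determination of cost effectiveness will be limited to those diagnosed with AF by 3 years using available claims data". The whole cohort comes next, in permissive terms: "A secondary analysis can evaluate the entire study population comparing a monitored approach to standard of care".

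On delivery, Protocol Section 4 (Monitoring Devices) says "All individuals randomized to active screening will receive a ZIO XT Patch", with wear in the first and last two weeks of the monitoring period. SAP Section 4 schedules two patches per person in both the immediate and the delayed group. Protocol Section 11 says "There is no cost to the subject for study participation".

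SAP Section 2 lists data sources that hold cost information. No analysis in SAP Section 3, endpoint in Section 5 or method in Sections 7 and 8 uses them for cost or cost-effectiveness, and no Bayesian model is described. The nearest item is utilization at 12 months, which Section 5 marks as still to be defined.

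**The concern.** The cost of a screening programme falls on everyone screened, and most of them do not have the condition. An analysis restricted to those diagnosed leaves out most of the people on whom the money is spent. Controls receive no study monitoring, so the omitted screening cost sits entirely in the monitored arm and the omission favours screening.

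Monitoring also reports other actionable rhythms to participants and, with permission, to their providers (Protocol Sections 4 and 5; SAP Section 5, safety endpoint 2). Any resulting care in people without AF is a consequence of screening. The restriction removes it even where it generates claims.

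At stake is whether a result presented as the cost-effectiveness of screening could be read against the stated objective. The primary detection endpoint is not affected.

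**Working it through.** **Inputs**

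- Monitored cohort 2,000 and matched controls 4,000 (Protocol Section 6; SAP Section 7).
- AF by 3 years: "10% prevalence of AF in both monitored and observational control arms" (Protocol Section 7).
- Scheduled patches: two per monitored person (Protocol Section 4; SAP Section 4).
- Unit cost of a patch and its reading: not given in either document.

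**Reproducing the plan's subset sizes.** SAP Section 7 states its calculation is "based on an expected prevalence of atrial fibrillation of 10% in both the actively monitored (i.e., n=200) and matched control cohorts (i.e, n=400". Check: 0.10 × 2,000 = 200 and 0.10 × 4,000 = 400. Both agree.

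**What the AF-only population leaves out**

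- Monitored people without an AF diagnosis: 2,000 − 200 = 1,800, or 90%.
- Scheduled patches in the whole cohort: 2,000 × 2 = 4,000.
- Scheduled patches in the AF subset: 200 × 2 = 400.
- Patches left out: 4,000 − 400 = 3,600, or 90%.

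**Screening load per AF case, if screening cost is counted per person analysed**

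- Whole cohort: 4,000 / 200 = 20 patches.
- AF subset only: 400 / 200 = 2 patches.
- Ratio: 20 / 2 = 10, which is 1 divided by the AF proportion.

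If the AF proportion were lower than 10%, the ratio would be larger. At 7% (the plan's 12-month figure for monitored people) it is 1 / 0.07 ≈ 14; at 5% (the 4-month figure) it is 1 / 0.05 = 20.

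The patch counts assume full compliance and exclude extra patches triggered by the wristband. Incomplete wear lowers the counts but leaves the ratio at 10 as long as patch use is similar with and without AF. The 200 include people diagnosed only through claims (SAP Section 4), so the split is AF-diagnosed versus not. It is not screen-positive versus screen-negative.

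**In money, under an assumed unit cost.** The range below is an assumption for illustration only.

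| Assumed screening cost per person | Whole cohort (× 2,000) | AF subset (× 200) | Left out (× 1,800) | Per AF case, whole cohort (÷ 200) | Per AF case, AF subset (÷ 200) |
|---|---|---|---|---|---|
| $200 | $400,000 | $40,000 | $360,000 | $2,000 | $200 |
| $500 | $1,000,000 | $100,000 | $900,000 | $5,000 | $500 |
| $1,000 | $2,000,000 | $200,000 | $1,800,000 | $10,000 | $1,000 |

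**The billing question.** There are two cases, and they rest on opposite premises, so their effects must not be added.

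1. Screening cost is captured for each person analysed, through claims or otherwise. The AF restriction then drops 90% of it, and the 10-fold figure applies.
2. Patches and reads generate no claims and only claims are used. Intervention cost is then missing from every population, including the whole cohort, and widening the population does not recover it.

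The documents do not say which case applies. The fix has to cover both.

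**The case against.** The strongest reply is that the plan already foresees a whole-population analysis, in the sentence right after the restriction, and that the overall-cost objective stands in its own right. Protocol Section 6 also plans a utilization comparison in the overall population, and SAP Section 3 lists utilization by cohort. This stands in part. A reader might infer that the plan rules out a whole-cohort cost analysis, or that the objective can never be met; the documents do not support that. But the whole-cohort step is optional and secondary, and the SAP does not take it up. Utilization at 12 months is neither cost nor a 3-year result.

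A second reply is that the protocol sets out no costing rule. It says whose claims are examined first, not how screening cost enters the Bayesian model. This also stands, and it is why the 10-fold figure is conditional.

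Third, a reader might infer that the intervention will be costed at zero because participants pay nothing. Protocol Section 11 covers only what participants pay. The insurer is the research partner, and its claims include equipment and professional encounters (SAP Section 2). Billing is simply not stated.

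Fourth, it is tempting to set the result against the figure of about $2,500 per additional case in Protocol Section 2, or to compute patches per additional case from the 12-month rates. The first is background on an earlier UK study; no comparison with it is planned. The second mixes horizons: at 3 years the plan assumes equal AF prevalence in both arms, so no additional cases are expected and that ratio is undefined.

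Finally, an AF-only analysis is a fair description of care after diagnosis. That is a reason to keep it as supportive.

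**Conclusion.** The point holds. The only firm rule for an analysis labelled as key uses a population that does not match its objective, and the SAP specifies no cost analysis that would correct this. On the plan's 10% assumption, about 1,800 of 2,000 monitored people and 3,600 of 4,000 scheduled patches fall outside it, together with any follow-up of other rhythm findings in people without AF. The documents give no size for that last part.

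The exclusion of 90% of monitored people rests only on the 10% figure. The 10-fold understatement of screening load per AF case also needs screening cost to be counted per person analysed, and similar patch use with and without AF; the figures of 2 and 20 patches assume full compliance. The possible absence of intervention cost from claims is a separate, open question. The matter concerns one secondary endpoint and should be corrected before the cost analysis is run.

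**What to change.** In Protocol Section 6, secondary efficacy endpoint 3, and in SAP Sections 3, 5 and 7:

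- Make the whole monitored cohort versus the whole matched control cohort the main 3-year cost and cost-effectiveness analysis, and write the model into the SAP.
- State whether patches and reads are billed to the insurer. Add screening costs that do not appear in claims by applying a stated unit cost to the patches sent, which the STSI enrollment database already records for each subject (SAP Section 2). Exclude any billed items from this addition, so that nothing is counted twice.
- Keep the AF-diagnosed subset as a supportive description of downstream care cost, labelled as such.

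The cost is wording in both documents, a justified unit cost and slightly more analysis work. No new data from participants are needed for the patch counts. The cost-effectiveness figure will look less favourable than an AF-only one.

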1. INTRODUCTION AND BACKGROUND

The mHealth Screening to Prevent Strokes (mSToPS) study is designed to determine whether mobile health monitoring can detect previously undiagnosed asymptomatic atrial fibrillation more effectively and lead to a reduction of thromboembolic events compared with usual care in a high-risk cohort identified and tracked using claims data.

The overarching objective of this study is to demonstrate that screening select individuals in their homes using wearable sensor technology can identify individuals with asymptomatic atrial fibrillation and that doing so will influence treatment and clinical outcomes.

Atrial Fibrillation Detection Objectives

- Identify a high-risk cohort optimized for screening based on claims data information.
- Determine the relative benefit of active screening compared to routine care (i.e., standard of care as defined by the medical care each patient is already receiving) for identifying new cases of atrial fibrillation after 4 months in the randomized cohort, and at one year in the combined monitored cohorts versus the matched observational control cohort
- As an exploratory analysis, compare the diagnostic capability of two different methods of rhythm screening – time-limited patch ECG monitoring versus long-term wearable pulse wave monitoring through photoplethysmography – for AF detection and tolerability.

Influence on Clinical Care

- Compare the rate of initiation of anticoagulation and other AF-specific therapeutic interventions (i.e. antiarrhythmic agents excluding beta-blockers and calcium channel blockers, cardioversions, ablation procedures or hospitalizations with a primary diagnosis of AF) at 12-months in the active monitoring cohort versus the matched observational control cohort.
- Compare the overall incremental costs of active monitoring for AF detection versus standard of care in the 3 years following the onset of monitoring.
- Identify the impact of active AF screening versus routine care on the time to first event of the following endpoints using claims data; A) among individuals diagnosed with new AF at 3 years following the initiation of screening, and B) the entire study cohort: utilizing claims data.
 - The combined endpoint of stroke/TIA, other systemic embolism, and/or myocardial infarction.

- In the Medicare population only, in who mortality data will be available, the combined endpoint of stroke/TIA, other systemic embolism, myocardial infarction and/or death
- The individual components of the combined endpoint.
- All hospitalizations.
- Hospitalizations for bleeding events.

